Following registration, patients should begin protocol treatment within 7 days of baseline AMT PET imaging. Issues that would cause treatment delays should be discussed with the Principal Investigator, [name] at [contact]; [contact], or contact the study coordinators. If a patient does not receive protocol therapy following registration, the patient's registration on the study may be cancelled. The study coordinator should be notified of cancellations as soon as possible.

Registration Process

To register a patient, the following documents should be completed by the research nurse or data manager and faxed or emailed to the study coordinator:

- Copies of required laboratory tests, scans.
- Signed patient consent form.
- HIPAA authorization form.
- Eligibility checklist.
- Completed registration form.

To complete the registration process, the study coordinator will:

• Register the patient on the study

Off-Study Criteria

• Patients will be considered to have gone off of study following the completion of the second AMT-PET scan. They may elect to continue telotristat ethyl therapy under the supervision of their physician as part of standard treatment. Cost of continued standard treatment will be charged to the patient's insurance and patient.

V. TREATMENT PLAN

AMT-PET Imaging

- Scan 1: Baseline within 7 days prior to the start of telotristat ethyl treatment.
- Scan 2: On day 9-14 of telotristat ethyl administration.
- Patients cannot eat protein containing foods for 6 hours prior to the AMT-PET studies, to ensure stable plasma tryptophan and large neutral amino acid levels during the duration of the study. They can have water and soft drinks.
- The final dose of telotristat ethyl on day 9-14 should be taken within 6 hours of the scan and should be taken along with high fat foods, but no protein. This may include oils, olives, low protein breads with margarine. The choice of such foods will be discussed with the patient at the time of enrollment. Note that this dietary restriction only applies for scan 2 since patients need to take telotristat ethyl with fat.
- Blood (approximately 3 tsp) will be drawn to measure drug levels and tumor hormone levels (including serotonin) in the blood prior to each scan. These will be done by the hospital and company laboratories.

Agent Administration

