Treatment will be administered on an outpatient basis. Reported adverse events and potential risks for telotristat ethyl are described in Section VI. No investigational or commercial agents or therapies other than telotristat ethyl may be administered with the intent to treat the patient's malignancy other than somatostatin analog (long-acting release [LAR], depot.

Agent	Dose	Route	Schedule
Telotristat ethyl	250 mg	Oral	Three times daily for 9-14 days prior to the second scan, with one dose or two doses depending on the time of Scan 2.*

*Patients may elect to stay on telotristat ethyl (250 mg tid) indefinitely following the completion Scan 2 if it is considered to provide benefit by their treating physician as part of the standard of care. As part of the study the patient will received 28 days of drug and may continue to use it and then obtain standard treatment on the agent if desired by the patient and their physician.

Benefits:

Telotristat ethyl (250 mg tid) daily compared to placebo has been shown to improve cancer related diarrhea (Kulke et al., 2017) and may slow tumor growth (Morse et al., 2020).

VI. ADVERSE EVENTS: LIST AND REPORTING REQUIREMENTS

This study will use the descriptions and grading scales found in the revised NCI Common Terminology Criteria for Adverse Events (CTCAE) version 4.0 will be utilized for AE reporting. All appropriate treatment areas should have access to a copy of the CTCAE version 4.0. A copy of the CTCAE can be

downloaded from the CTEP web site (http://ctep.cancer.gov/protocolDevelopment/electronic_applications/ctc.htm#ctc_40).

Reporting Adverse Events

In the unlikely event that any immediate toxicity is found during the course of treatment, it will be recorded and reported as described below. Given the dose of drug, no measurable delayed toxicity is expected.

		Reporting Obligation for A, B, and
	Reaction	C
А.	All life-threatening events (Grade 4), which may be due to drug	Within 24 hours (note 1)
В.	All fatal events (Grade 5) while on study (or within 24 hour	Written report to follow within 10
	of treatment).	working days (note 1).
C.	First occurrence of any previously unknown clinical event (regardless of grade).	(Note 2 and 3)

- Note 1: Telephone number available 24 hours daily: [name] page [contact] [name], [contact] (Recorder after hours). Also may report to [contact] and [contact]
- Note 2: A list of all known toxicities can be found in the protocol document or consent form.

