- Note 3: Reactions judged *definitely* not treatment-related should not be reported.
- Information about all adverse events, whether volunteered by the subject, discovered by
 investigator questioning, or detected through physical examination, laboratory test or other
 means, will be collected and recorded on the Adverse Event Case Report Form and followed as
 appropriate. An adverse event is any undesirable sign, symptom or medical condition occurring
 after starting even if the event is not considered to be related.
- Medical conditions/diseases present before starting study treatment are only considered adverse events if they worsen after starting study treatment (any procedures specified in the protocol).
- Any serious adverse event occurring after the patient has provided informed consent and until 4 weeks after the second scan of must be reported.
- Adverse events occurring before starting study treatment but after signing the informed consent form are recorded on the Medical History/Current Medical Conditions Case Report Form.
- Abnormal laboratory values or test results constitute adverse events only if they induce clinical signs or symptoms or require therapy, and are recorded on the Adverse Events Case Report Form under the signs, symptoms or diagnosis associated with them.

Adverse Event (AE) Characteristics

Serious adverse events

A serious adverse event is an undesirable sign, symptom or medical condition which:

- 1. Is fatal or life-threatening.
- 2. Required or prolonged hospitalization
- 3. Results in persistent or significant disability/incapacity
- 4. Constitutes a congenital anomaly or a birth defect
- 5. Are medically significant, may jeopardize the subject and may require medical or surgical intervention to prevent one of the outcomes listed above

Not considered to be serious adverse events are hospitalizations for the:

- 1. Routine treatment or monitoring of the studied indication, not associated with any deterioration in condition.
- 2. Treatment, which was elective or pre-planned, for a pre-existing condition that did not worsen
- 3. treatment on an emergency, outpatient basis for an event **not** fulfilling any of the definitions of serious given above and **not** resulting in hospital admission

Commonly Reported Side Effects of telotristat ethyl

From the package insert.

- nausea 13%,
- headache 11%
- increased liver function test (GGT) 9%, possibly indicating liver damage
- depression 9%

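### Minor, cheap improvement: serious-event reporting is timed from Scan 2 rather than from the last study-supplied dose, so a patient who finishes the 28-day supply and stops has 9-14 days of cover afterwards instead of 28

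*Combined protocol and SAP*

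**What the plan says.** Four parts of the combined protocol and SAP bear on this.

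- **Section VI, Reporting Adverse Events**, sets the window: "Any serious adverse event occurring after the patient has provided informed consent and until 4 weeks after the second scan of must be reported". It is counted from the scan, and the last dose is not mentioned.
- **Section V, AMT-PET Imaging**, fixes the scan date: "Scan 2: On day 9-14 of telotristat ethyl administration".
- **Section V, Agent Administration**, footnote to the dosing table, gives the supply: "As part of the study the patient will received 28 days of drug and may continue to use it". Standard treatment is described as following that supply.
- **Section IV, Off-Study Criteria**, states: "Patients will be considered to have gone off of study following the completion of the second AMT-PET scan". On continued drug it adds: "They may elect to continue telotristat ethyl therapy under the supervision of their physician as part of standard treatment".

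Other rules in Section VI also matter. The reporting table covers "All life-threatening events (Grade 4), which may be due to drug" (rule A) and "First occurrence of any previously unknown clinical event (regardless of grade)" (rule C), neither with an end date. Recording of all adverse events on the case report form has no end date either. The section also says: "Given the dose of drug, no measurable delayed toxicity is expected". Section VIII, under Study Duration, gives each patient at least three months of follow-up.

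**The concern.** A safety window normally follows exposure. Here it follows an imaging visit, while drug supplied by the study can be taken for two weeks or more after that visit. The protocol has chosen a four-week tail, but only a patient who stops at Scan 2 receives all of it after the last dose. A patient who finishes the supply has part of that tail used up while still dosing.

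A patient who starts drug but never has Scan 2 has no defined end to serious-event reporting, because the scan is the only anchor. Section VI tells patients to discontinue for severe constipation or severe abdominal pain, so stopping before day 9 is foreseeable.

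What is at stake is even-handed serious-event reporting in a pilot of six evaluable patients. The primary endpoint is fixed once Scan 2 is done and is not affected.

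**Working it through.** The plan gives no figure for cover after the last dose, so there is none to reproduce. Its one design calculation, the lower confidence limit of 0.201 in Section VIII, does not bear on this point.

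**Inputs**
- Scan 2 day, s: 9 to 14 (Section V).
- Serious-event tail: 4 weeks = 28 days after Scan 2 (Section VI).
- Study supply: 28 days (Section V). Assumption: counted from the first dose as day 1 and taken without a break, so the last supplied dose is on day 28.

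**Supplied drug remaining at Scan 2**, 28 − s:
- s = 9: 28 − 9 = 19 days (19/28 = 68%).
- s = 14: 28 − 14 = 14 days (14/28 = 50%).

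**Day the window closes**, s + 28:
- s = 9: day 37.
- s = 14: day 42.

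**Cover after the last supplied dose**, closing day minus last-dose day:

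| Patient | Scan 2 on day 9 | Scan 2 on day 14 |
|---|---|---|
| Stops at Scan 2 | 37 − 9 = 28 days | 42 − 14 = 28 days |
| Takes full supply, then stops | 37 − 28 = 9 days | 42 − 28 = 14 days |

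**Illustration.** Take a Grade 3 admission for constipation 15 days after the last supplied dose (a day chosen for the example). It is serious because it requires hospitalization. In a patient who stopped at Scan 2 it falls on day 9 + 15 = 24 or 14 + 15 = 29, inside the window. In a patient who finished the supply it falls on day 28 + 15 = 43, after the window has closed for any permitted scan day. Rule A does not apply, as the event is not Grade 4. Rule C does not apply, as constipation is a listed reaction. The event would still be recorded as an adverse event, but the serious-event rule would not require a report.

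**With the window tied to the later of the two dates**
- Full supply: 28 + 28 = day 56. Days added: 56 − 42 = 14 to 56 − 37 = 19.
- Stop at Scan 2: still day 37-42, nothing added.
- Three months taken as about 90 days from the first dose (assumption): 90 − 56 = 34 days to spare, so the stated follow-up already contains day 56.

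**Other reading of the supply.** If the 28 days were counted from Scan 2, the last supplied dose would fall on day s + 28, the day the window closes, leaving 0 days of cover. Counting from the first dose is the more natural reading and gives the milder result.

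**The case against.** The strongest case for leaving the text alone has four parts.

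1. **No supplied dose is uncovered.** An uninterrupted supply ends on day 28 and the window closes on day 37 at the earliest. This stands. A reader might infer that patients take study drug outside safety reporting. The documents do not support that: it would need a long dosing pause, and they give no rate or length for one.
2. **Scan 2 is a coherent anchor.** Required dosing runs up to the scan, and continuation is described as standard care with an approved drug. This stands in part. The same footnote makes the 28-day supply part of the study and places standard treatment after it. For a patient who moves on to prescribed drug, day 28 is not a last dose, so the 9-14 versus 28 contrast applies only to those who finish the supply and stop.
3. **Little would be lost.** No measurable delayed toxicity is expected. All adverse events are recorded without an end date, and Section IX has them discussed at monthly meetings, with quarterly reports to the monitoring committee. This stands and keeps the point minor: what may be missed is the serious-event report, not the record.
4. **The follow-up rules can be read together.** A reader might infer that going off study at Scan 2 contradicts the three-month follow-up. The documents do not establish that. Section VI already carries safety reporting past the off-study point, and the three months appears only in a planning sentence on study duration. The wording is unreconciled, which one clarifying sentence can settle.

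**Conclusion.** The point holds as a minor, inexpensive improvement. With the 28-day supply counted from the first dose and taken without a break, a patient who finishes it and stops has 9-14 days of serious-event cover after the last supplied dose, against 28 days for one who stops at Scan 2. Reporting also has no defined end for a patient without Scan 2; that is an undefined end, not an absence of cover.

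This is a matter of applying the protocol's own four-week tail equally. It is no evidence of unmonitored dosing or of expected harm, and it has no bearing on the SUVmax endpoint, the sample size or any analysis.

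**What to change.** **Section VI, Reporting Adverse Events.** Replace the end of the serious-event window with wording such as: *Serious adverse events will be reported from consent until the later of 4 weeks after Scan 2 and 4 weeks after the last dose of study-supplied telotristat ethyl. For a patient without Scan 2, reporting ends 4 weeks after the last study-supplied dose.*

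**Section IV, Off-Study Criteria.** Keep the off-study date and add: *Off-study status at Scan 2 ends protocol treatment and imaging but not the safety collection in Section VI.*

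**Leave unchanged** the three-month minimum follow-up in Section VIII and the open-ended recording of all adverse events. Shortening either would remove follow-up that the protocol already provides.

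**Cost.** Two wording changes and about one extra safety contact per patient, made while the patient is under the treating physician's care; the contact must also establish the date of the last supplied dose. The window grows by 14-19 days for a patient who takes the full supply and not at all for one who stops at Scan 2. Because day 56 lies within the stated follow-up, the planned 15-18 months need not change.

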2017-144 Monitoring Telotristat Ethyl Inhibition of Tryptophan hydroxylase (TPH) in Neuroendocrine Tumors Using α -[¹¹C]methyl-L-tryptophan (AMT)-PET Version 1: 11/27/17; Revised 09/10/19; Revised 05/26/20

Table of contents:

	Protocol summary	2
١.	Objectives	3
II.	Background	3
III.	Patient selection	6
IV.	Registration procedures	7
٧.	Treatment plan	8
VI.	Adverse events	8
VII.	Measurement of effect (AMT-PET)	11
VIII.	Statistical plan	12
IX.	Data and safety monitoring	13
Х.	References	15

Principal Investigator: [name], PhD [contact]; [contact] Email: [contact] [name]

Co- Investigator: [name], PhD [name], PhD [name] [name] [name], MSN, CNP [name] - Biostatistician

PROTOCOL SUMMARY

OBJECTIVES:

Primary objective is to show that telotristat ethyl (Xermelo[™]), a recently FDA-approved TPH inhibitor drug, will decrease tumoral AMT uptake and trapping as compared to values measured at baseline before the start of treatment. Secondary objective is to show that neuroendocrine tumors (NETs) will have increased AMT uptake on positron emission tomography (PET), as compared to surrounding non-tumor tissue at baseline.

PATIENT POPULATION:

- 1. Histopathologically confirmed, well-differentiated metastatic NETs.
- Patients receiving stable-dose somatostatin analogs (SSAs, long-acting release [LAR], depot) for > 3 months before enrollment.

STUDY DESIGN:

Imaging will be done with AMT-PET/CT, under separate protocol 2011-053, at baseline and after 9-14 days treatment on telotristat ethyl, 250 mg po three times daily.

EVALUATION:

Prior to PET imaging: Physical exam, CBC and Multiphasic (electrolytes, renal and liver function) drawn within 28 days of start of the study as part of routine care. Radiology testing to measure tumor size (for example, CT scans, MRI scans, PET scans) which are part of routine care. Scan may be done within 8 weeks of the start of the study. A negative urine or blood pregnancy test must be obtained in women with child bearing potential on the day of the first PET scan.

PRIMARY and Secondary ENDPOINTS:

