The measurement of the uptake and retention of AMT will be quantitated by maximum standardized uptake values (SUVmax) and compartmental modeling (in tumors with the left ventricle of the heart in the field-of-view) before and after treatment with telotristat ethyl. The proportion of patients whose reduction in AMT uptake between baseline and follow-up is \geq 20% will be the primary endpoint. We will also assess if the NET is visible above background at baseline and will also quantify the percent difference in AMT uptake between the tumor mass and background. Using time-activity curves, we will also identify the optimal time frame where tumoral AMT uptake peaks.

STATISTICAL PLAN:

This is a single arm single institution prospective proof-of-concept study. The proportion of patients, who achieved SUVmax reduction of 20% or more, will be estimated and exact (Clopper-Pearson) confidence interval will be calculated. Paired t test will be used for pre- and post- treatment SUVs if normality assumption holds. The relationship of one PET parameter to another will be visualized with scatter plot and measured using linear regression models.

I. OBJECTIVES

- Primary Objective: The primary objective of this pilot study is to evaluate the effect of telotristat ethyl treatment in patients with advanced neuroendocrine tumors (NETs) using α-[¹¹C]methyl-L-tryptophan (AMT)-positron emission tomography (PET) as measured by changes in tumor maximum standardized uptake value (SUVmax).
- 2. Secondary Objectives:
 - **a.** Show that NETs will have increased AMT uptake on PET, as compared to surrounding nontumor tissue at baseline
 - **b.** Use compartmental modeling (in tumors with the left ventricle of the heart in the field-of-view) to measure change in AMT retention.
 - c. Measure change in AMT retention as SUVmean

II. BACKGROUND

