- peripheral edema (leg swelling) 7%
- flatulence 7%
- decreased appetite 7%
- fever 7%

In another placebo-controlled clinical trial of patients with carcinoid syndrome diarrhea and less than 4 bowel movements per day, the following additional adverse reactions, not listed above, of abdominal pain (including upper and lower abdominal pain, abdominal distention and gastrointestinal pain) and constipation were reported in at least 5% of patients in the telotristat ethyl treated group and at an incidence greater than placebo. Discontinue telotristat ethyl if severe constipation or severe persistent or worsening abdominal pain develops

Less Common Adverse Reactions:

The following is a list of adverse reactions occurring in less than 5% of patients receiving telotristat ethyl during the 12-week placebo-controlled period of the clinical trial:

Investigations: increased alkaline phosphatase, increased alanine aminotransferase, and increased aspartate aminotransferase.

Fecaloma was reported in one patient treated with telotristat ethyl during the 36-week open-label extension period following the 12-week double-blind period of the trial.

'Attribution' of the AE will be defined by the investigative team

- Definite The AE *is clearly related* to the study treatment
- Probable The AE *is likely related* to the study treatment
- Possible The AE *may be related* to the study treatment
- Unlikely The AE *is doubtfully related* to the study treatment
- Unrelated The AE *is clearly NOT related* to the study treatment

VII. MEASUREMENT OF EFFECT: AMT PET SCAN ACQUISTION AND ANALYSIS

Baseline AMT-PET scan will be obtained within 7 days of the start of telotristat ethyl 250 mg po tid and then again 9-14 days after the start of treatment under protocol 2011-053 as described below.

PET imaging will be performed using a GE Discovery STE PET/CT system (GE Medical Systems, Milwaukee, WI), located at the PET Center, Children's Hospital of Michigan. Patients will be imaged in a supine (on their back) position on a PET/CT scanner in a high-sensitivity mode.

Patients cannot eat protein containing foods for 6 hours prior to the AMT-PET studies, to ensure stable plasma tryptophan and large neutral amino acid levels during the duration of the study. The final dose of telotristat ethyl should be taken within 6 hours of the scan and should be taken along with high fat foods, but no protein (as described in the Treatment Plan).

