A venous line will be established for injection of AMT tracer (0.1 mci/kg). All PET images will be corrected for attenuation using the CT scan. After injection a CT scan is performed, immediately followed by a 60-minute dynamic PET scan of the area of interest that includes the tumor. The total dose for the PET/CT scan will be in compliance with guidelines for research studies prescribed by the Code of Federal Regulation.

Quantitative assessment of AMT tumor uptake. The AMT uptake in ROIs representing tumor and non-tumor tissue will be characterized in the following two ways:

1. Standardized uptake values (SUVs): The SUV calculation relates tracer concentration in tissue to the dose injected and the subject's mass (SUV = tissue concentration in ROI /injected dose per weight). First, decay-corrected time-activity curves will be generated to evaluate the tumoral accumulation and washout of the tracer during the scanning period. Since all subjects receive the same injected dose based upon weight (0.1 mCi/kg), the SUV images will be directly obtained by averaging values from frames of the dynamic image sequence during which time there is the most metabolic product. The timing of these frames will be determined after examination of the time-activity curves to identify the optimal time frame when tracer uptake reaches a plateau. The Standard Uptake Value maximum (SUVmax) will measure the most active pixel in the tumor and the two adjacent planes. Change in SUVmax will serve as the primary aim. Regions of Interest (ROIs) for the SUVmean will be drawn using isocontours set at 50% of the SUVmax. Results will be indicated as percent change in the uptake between the two scans.

2. Compartmental modeling (in tumors with the left ventricle of the heart in the field-of-view). In addition to the semi-quantitative SUV analysis, in tumors where the left ventricle of the heart is in the field-of-view, we will also assess the data with tracer kinetic analysis using a 3-compartment model, as described in our previous studies in lung and breast tumors (Juhasz et al., 2009; 2012). This analysis will allow a more detailed analysis of tumoral tracer transport and trapping parameters at baseline and their changes after TPH inhibitor treatment.

3. Primary endpoint and secondary endpoints:

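### Section VII starts the dynamic PET only after injection and CT, so the left-ventricle curve that the compartmental analysis (objective 2b) appears to rely on would lack its first part

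*Combined protocol and SAP*

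**What the plan says.** - **Acquisition order (Section VII).** "After injection a CT scan is performed, immediately followed by a 60-minute dynamic PET scan of the area of interest that includes the tumor". The CT serves attenuation correction. The same section gives no time from injection to the first PET frame.
- **Kinetic analysis (Section VII, item 2).** A 3-compartment model is applied "in tumors where the left ventricle of the heart is in the field-of-view", with the method "as described in our previous studies in lung and breast tumors". It is meant to yield "tumoral tracer transport and trapping parameters at baseline and their changes after TPH inhibitor treatment".
- **Objective (Section I, 2b).** Compartmental modelling is used "to measure change in AMT retention".
- **Governing protocol.** The protocol summary places imaging "under separate protocol 2011-053". The opening of Section VII says the scans are done "under protocol 2011-053 as described below", so Section VII is offered as the description of the acquisition.
- **Blood sampling (Section V).** The only blood draw is "drawn to measure drug levels and tumor hormone levels (including serotonin) in the blood prior to each scan". No sampling of tracer activity during the scan is mentioned.

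**The concern.** A compartmental model needs the tracer concentration in blood from the moment of injection. Requiring the left ventricle to be in view has no evident purpose in a kinetic analysis other than to read that concentration from the images. If PET begins only after an intervening CT, the ventricular curve has no data from injection to the first frame, which is when a bolus peaks. The two parts of Section VII then do not fit together.

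The transport rate K1 depends most on the early curve; net uptake Ki depends on it less. Objective 2b is a within-patient change, so a gap of the same length at both scans largely cancels in Ki, but gaps of different length can produce a change that is not real. The protocol fixes no interval. A missed early curve cannot be recovered after the scan.

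**Working it through.** **Reading the text.** The order is injection, CT, PET. The first frame therefore starts d minutes after injection, where d is at least the CT duration and so greater than 0. The ventricular curve has no data from 0 to d. The Section V draw precedes each scan and is for drug and hormone levels, so it cannot fill the gap. The documents give neither d nor the injection duration, so there is no figure of the plan's to reproduce, and the size of the loss can only be illustrated.

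**Illustration: all inputs below are assumptions.** Noise-free irreversible model with blood volume 0:

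dCf/dt = K1·Cp − (k2 + k3)·Cf, dCt/dt = k3·Cf, Ki = K1·k3/(k2 + k3).

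Rates K1, k2, k3 (per min) and the resulting Ki:
- A: 0.10, 0.15, 0.03; Ki = 0.10 × 0.03/0.18 = 0.0167
- B: 0.05, 0.08, 0.02; Ki = 0.05 × 0.02/0.10 = 0.0100
- C: 0.20, 0.25, 0.04; Ki = 0.20 × 0.04/0.29 = 0.0276

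Blood inputs (t in min):
- (i) bolus: (851.1x − 42.7)exp(−4.134x) + 21.9exp(−0.119x) + 20.8exp(−0.0104x), with x = t − 0.3 and negatives set to 0
- (ii) a 0.5-min linear ramp, then 80exp(−2x) + 15exp(−0.15x) + 12exp(−0.012x), with x = t − 0.5
- (iii) input (i) averaged over a 2-min infusion

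Frames from PET start: 12×10 s, 6×30 s, 5×1 min, 4×2.5 min, 8×5 min (60 min in all). The input before PET start is set to 0, and the model is refitted by least squares weighted by frame duration.

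**Share of the 0–60 min input area missed (%)**

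| Input | 0.5 min | 1 min | 2 min | 3 min |
|---|---|---|---|---|
| (i) | 1.1 | 5.1 | 9.4 | 12.7 |
| (ii) | 4.0 | 9.6 | 15.2 | 18.8 |
| (iii) | 0.0 | 0.9 | 4.6 | 9.3 |

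**Bias in Ki (%), weighted fit**

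| Input, rates | 0.5 min | 1 min | 2 min | 3 min |
|---|---|---|---|---|
| (i) A | 1.2 | 5.6 | 10.1 | 13.4 |
| (i) B | 2.2 | 9.6 | 16.0 | 20.3 |
| (i) C | 0.9 | 4.5 | 8.7 | 10.9 |
| (ii) A | 3.4 | 8.9 | 15.0 | 19.0 |
| (ii) B | 5.9 | 14.3 | 22.0 | 26.6 |
| (ii) C | 2.8 | 7.3 | 11.7 | 13.3 |
| (iii) A | 0.0 | 0.9 | 4.8 | 9.9 |
| (iii) B | 0.1 | 1.7 | 8.5 | 15.8 |
| (iii) C | 0.0 | 0.7 | 3.9 | 8.4 |

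**Other analyses**
- K1, weighted: 0% to +44% at 0.5 min; +5% to about +240% at 1 min.
- Ki, unweighted: 0% to +14% at 0.5 min; +2% to +35% at 1 min. Half of the unweighted fits at 2–3 min (18 of 36) hit a parameter bound and are not reported. Among weighted fits, 2 of 18 at 2 min and 5 of 18 at 3 min also hit one, so those columns are less secure.
- Patlak slope (frames from 20 min after PET start): about 0% to +3% at 0.5 min, 0% to +7% at 1 min, +4% to +14% at 3 min.
- Missed input filled with a straight line from zero to the first observed value, weighted fit: about −1% to +8% at 1 min and +3% to +17% at 3 min.

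**Change between scans, equal gaps.** Cutting k3 by 40% gives a true Ki fall of 35.7% (A), 34.8% (B) and 36.5% (C). For example, in B, 0.05 × 0.012/0.092 = 0.00652, and 1 − 0.00652/0.0100 = 34.8%. Over the 36 weighted cases (3 inputs, 3 rate sets, 4 gaps) the estimated fall is between 5.2 points too small and 1.2 points too large. In 28 of the 36 the shift is 2 points or less; the 8 larger shifts all come from rate set B. With Patlak the shift is about 1 point at most; unweighted, it reaches about 10 points for gaps up to 1 min.

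**No true change, unequal gaps.** The spurious change is (1 + bias at scan 2)/(1 + bias at scan 1) − 1. For input (i), rates A, and gaps of 1 then 2 min: 1.101/1.056 − 1 = 4.3%. Across all nine settings the range is +3.2% to +6.8% (weighted) or +1.7% to +4.0% (Patlak). For gaps of 0.5 then 1 min it is +0.7% to +7.9% (weighted) or +0.2% to +3.9% (Patlak).

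**The case against.** The details of acquisition and input may sit in protocol 2011-053 or in the cited lung and breast studies, none of which is available here, and the sentence may be loose wording rather than practice. Nowhere does the protocol say that the left ventricle is the input; that is an inference. On this view the plan is merely unclear about when PET starts. The effect on the stated objective is also modest: 2b is a change, and with equal gaps most shifts in Ki are under 2 points. One procedure on one scanner, with PET directly after CT, constrains the gap even without a number. Setting the missed input to zero is the extreme choice. Finally, the analysis concerns an unknown subset, possibly none, of 6 evaluable patients, and Section VIII sets no test or threshold for kinetic parameters.

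Much of this stands as a limit on size. It does not remove the point. Section VII presents itself as the description of the acquisition, the inference about the ventricle is a strong one, and no other input is given. If 2011-053 says something different, the two texts disagree and need reconciling anyway. Item 2 also promises transport parameters, for which the bias is not modest.

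**Conclusion.** The concern holds. Followed as written, Section VII loses the early part of the only tracer input that the protocol implies, and this undermines the kinetic analysis behind objective 2b. The size cannot be derived from the documents. Under the assumptions above it ranges from near zero (slow infusion, short gap) to roughly a quarter of Ki at a 3-minute gap, with much larger errors in K1. The effect on the change in Ki is small if the gaps are equal, and a few per cent if they differ by half a minute to a minute.

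The conclusion rests on the ventricle being the input source and on 2011-053 and the cited methods not supplying another. It is worth correcting but does not threaten the trial's main result: the primary SUVmax endpoint is not affected by this mechanism.

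**What to change.** 1. Reconcile the acquisition sentence in Section VII with item 2 and with protocol 2011-053.
2. State the source of the blood input and the time from injection to the first PET frame, the same at both scans.
3. Unless 2011-053 or the cited methods supply another input, reword so that the attenuation CT precedes injection and the dynamic PET starts at injection and runs for 60 minutes, at both scans. In that case, name the left ventricle in the dynamic frames as the input source.

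**Cost.** In this protocol, a change of wording. Nothing in the text requires the CT to follow injection. Inclusion criterion 5 already asks for 70 minutes in the scanner, and 70 − 60 = 10 minutes remain for the CT. No scan, radiation or visit is added. If injection before CT is the actual practice under 2011-053, that protocol's procedure would have to change as well.
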